The dosage of the study medication will be adjusted upon hospital discharge of the patients as follows. Patients randomized to rivaroxaban 20 mg OD will reduce daily dosage to 10 mg OD, provided that they were not diagnosed with a condition requiring continued therapeutic anticoagulation.

Patients randomized to the SOC arm will receive SOC with prophylactic LMWH or UFH according to local practice, provided that they were not diagnosed with a condition requiring continued therapeutic anticoagulation. Study visits are terminated 7, 35, and 60 days post randomization. The 60 day EOS visit will be done as a telephone visit.

If a subject has a suspected efficacy or bleeding outcome event during the study, the treating physician should clinically judge and follow established guidelines to apply best medical care.

The primary endpoint is to assess the effect of rivaroxaban compared with standard of care (SOC) with the use of prophylactic low molecular weight heparin (LMWH) or unfractionated heparin (UFH) on D-dimer as a clinical marker for a worse clinical outcome at day 7 post randomization adjusted for baseline measurement in patients with moderate to severe COVID-19.

The co-primary endpoint is to evaluate the impact of rivaroxaban compared with standard of care (SOC) with the use of prophylactic low molecular weight heparin (LMWH) or unfractionated heparin (UFH) on a seven-category ordinal scale recommended by the WHO as a measure of clinical benefit at day 7 post randomization in patients with moderate to severe COVID-19.

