## TIME AND EVENTS SCHEDULE

Period	Screening a	Randomization	Therapeutic anticoagulation		Prophylactic anticoagulation	Follow-up
			Day 7	Discharge b		
Visit	Screen	Rand	Day 7	Discharge b	Endpoint visit	EOS visit c
Days from randomization		0	7	Discharge day (variable)	35 days post Rand	60 days post Rand
Day window	-3/ 0	0	-2/ +1	-2/ 0	-0/+5	-3/+4
Informed consent	X					
Inclusion/Exclusion d	X	X				
SARS-CoV-2 test + e	X					
Physical Exam and Vitals f	X		X	X	X	(X)
D-dimer g,h	X		X	X	X	(X)
hs-cTnT g,h	X					
Demographics	X					
Medical History	X					
Hemoglobin/Platelet count g	X		X	X	X	
Serum creatinine g	X		X	X	X	
Serum/urine Pregnancy i	X					
Further safety blood assessment j	X		X		X	
ECG	X		X	X	(X)	
Registration		X				
Dispense Study Drug		X	X	X		
Study drug accountability			X	X	X	
Adverse Events		X	X	X	X	X
CTPA k			(X)	(X)	(X)	
Seven-category ordinal scale			X	X	X	X
Endpoint assessment			X	X	X	X
Concomitant Medications	X	X	X	X	X	X
Blood sampling l		(X)	(X)	(X)	(X)	(X)

EOT= end of treatment; EOS = end of study; hs-cTnT= high sensitive cardiac troponin T; ECG= electrocardiogram; CTPA= Computed tomography pulmonary angiogram

- The time between the confirmation of a positive SARS-CoV-2 test and screening should not exceed 14 days.
- If the patient is discharged later than day 10 post randomization a discharge visit becomes mandatory.
- This visit may be performed as telephone visit.
- Screening inclusion / exclusion criteria should be assessed and verified at randomization.
- The subject might be eligible for the study, if the SARS-CoV-2 polymerase chain reaction (PCR) test had been positive within 14 days prior to randomization. There is no need to repeat the SARS-CoV-2 PCR test in the screening period.

- f. Vital signs include pulse, blood pressure, temperature, respiratory rate and oxygen saturation.
- g. Hemoglobin, platelet count, serum creatinine, D-dimer, hs-cTnT and white blood cell differential will be obtained by the local laboratory.
- h. D-dimer and hs-cTnT values from up to 3 days prior to screening can be used.
- i. Pregnancy test must be performed in women of child-bearing potential.

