In case of hospitalization for more than 7 days, the therapeutic treatment with rivaroxaban will be continued for the duration of the hospital stay until discharge. After at least 7 days of therapeutic treatment with rivaroxaban or after hospital discharge, whatever is the event that occurs later, the study dose of rivaroxaban will be adjusted as follows: Patients randomized to rivaroxaban 20mg OD will reduce daily dosage to 10 mg OD, provided that they were not diagnosed with a condition requiring continued therapeutic anticoagulation. Thromboprophylaxis therapy will be given for 28 days up to day 35 post randomization or even longer. If the patient cannot be discharged from the hospital prior to day 35 post randomization, the thromboprophylaxis phase will also start upon hospital discharge, but is then shorter than 28 days, because the study ends latest at day 60 post randomization. The complete end of study (EOS) visit will be done via phone call 60 days post randomization. No study medication will be given thereafter.

After the study, the patients continue to receive medical therapy according to local practice.

If the clinical condition of a hospitalized patient deteriorates and admission to ICU with possible invasive ventilation will become necessary, treatment with rivaroxaban should be discontinued for the ICU period and the patient switched to parental or subcutaneous anticoagulation following best local practice. After clinical improvement and discontinuation of invasive ventilation, the anticoagulation mentioned above can be replaced by study drug rivaroxaban 20 mg OD (15 mg for subjects with an  $eGFR \geq 30$  mL/min/1.73m^2 and <50 mL/min/1.73m^2) at the discretion of the clinically responsible physician.

Patients randomized to the SOC treatment arm will receive SOC during the time of hospitalization or for at least 7 days, whatever is later. SOC constitutes of prophylactic doses of LMWH or UFH, according to the local practice and decision of the physicians of the respective trial site. Study visits are terminated 7, 35, and 60 days post randomization in all patients. The latter will be done via phone call if applicable. For the hospitalized patients who are discharged later than 10 days post randomization, an additional discharge visit will be done at the day of discharge (-2 days).

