### 35 days post randomization visit

A visit will be conducted in all patients at day 35 (-0 / +5 days) post randomization.

Physical exam and clinical status review for suspected outcome events will be completed. Adverse events will be collected as specified in Section 12, outcome assessment will also be performed, and concomitant medication will be collected as specified in Section 8. Subject counseling provided at the randomization visit will be repeated in detail including also:

- The need to seek for medical attention if any of the symptoms of above-mentioned diseases are developed
- The need to inform the treating health care providers about study participation
- The need to inform the investigator as soon as symptoms develop

EDTA and heparin blood will be drawn to determine hemoglobin/platelets counts, D-dimer, creatinine, AST, ALT, INR, aPTT, hs-CRP, NT-pro-BNP and will be sent to local laboratory, if not already taken according to the routine medical care.

If lung imaging is part of the local routine, it is encouraged to be done as a CTPA to assess the presence of PE. An ECG will optionally be performed.

The clinical condition of the patient will be documented using the seven-category ordinal scale recommended by the WHO for patients with respiratory infections (23-25).

The drug accountability should also be done during this visit.

If patient signed the ICF for optional bio-banking serum, heparin, citrate and EDTA blood will be drawn and sent to the Charité, Campus Benjamin Franklin, Berlin, for coagulation analysis and bio-banking.

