### **Follow-up**

#### EOS Visit (60 days post randomization)

EOS visit will be conducted as a telephone visit, but – if the patient is still hospitalized - can also be done at the clinic. Adverse events will be collected as specified in Section 12, outcome assessment will also be performed, and information about concomitant medication will be collected as specified in Section 8. Subject counseling provided at the randomization, and in hospital visits will be again repeated in detail:

- The need to seek for medical attention if any of the symptoms of above-mentioned diseases are developed
- The need to inform the treating health care providers about study participation
- The need to inform the investigator as soon as symptoms develop

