### 11.3 Secondary Efficacy Endpoint

The secondary combined endpoint includes

Time to first event of either

- Venous thromboembolism (VTE) (deep venous thrombosis (DVT) and/or fatal or non-fatal pulmonary embolism (PE))
- Arterial thromboembolism
- New myocardial infarction (MI)
- Non-hemorrhagic stroke
- All-cause death
- Progression to intubation and invasive ventilation

Time to first event of either of the components of the secondary composite endpoint will be analyzed using a Cox proportional hazards regression model with treatment and the stratification variables of the randomization (site, gender (male, female, diverse), age (< 65 versus  $\geq$  65 years), kidney function (eGFR  $\geq$  30 mL/min/1.73m^2 and < 50 mL/min/1.73m^2 versus eGFR  $\geq$  50 mL/min/1.73m^2), history of CAD or heart failure (yes/no), oxygen demand on admission to the hospital (supplementary oxygen required versus not required), setting (outpatients versus hospitalized patients)) as factors. The treatment effect will be reported as hazard ratio (HR) with 95% confidence interval and p-value for the null hypothesis H0: HR=1. The primary endpoint will be visualized as Kaplan-Meier curves. Sensitivity analyses will explore the robustness of these analyses.

The analyses of the time-to-event outcomes among the secondary endpoints (such as time to VTE, time to arterial thromboembolism, time to new MI, time to non-hemorrhagic stroke, time to all-cause death, time to progression to intubation and invasive ventilation) will follow the same lines as the analysis of the composite outcome, i.e. survival analyses comprising Cox proportional hazard regression models and Kaplan-Meier curves. Death will be treated as a competing event except when analyzing all-cause death, naturally.

Longitudinal D-dimer measurements assessed at day 7, 35 and 60 will be analyzed on the logarithmic scale using a mixed model for repeated measures (MMRM) approach. The model will include treatment, visit, treatment-by-visit interaction and stratification variables of the randomization as factors as well as logarithmic D-dimer baseline value as covariate. The residuals will be assumed to follow a multivariate normal distribution with unstructured covariance matrix. LS means of the group means and their differences will be computed for the various timepoints and reported with 95% confidence intervals.

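### The longitudinal D-dimer model reports a day-60 treatment difference, but the day-60 visit is planned as a telephone visit, so that estimate will probably rest on a small, selected subset

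*Protocol*

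**What the plan says.** **The analysis.** Protocol section 11.3, repeated in the Synopsis under Secondary Efficacy Endpoints, plans: "Longitudinal D-dimer measurements assessed at day 7, 35 and 60 will be analyzed on the logarithmic scale". The model is an MMRM with treatment, visit, their interaction, the randomization strata and log baseline D-dimer, with an unstructured covariance matrix. On reporting it says: "LS means of the group means and their differences will be computed for the various timepoints and reported with 95% confidence intervals". Day 60 is therefore one of the times at which a treatment difference is promised.

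**The visit.**
- Synopsis, Overview of Study Design: "The 60 day EOS visit will be done as a telephone visit".
- Section 3.1: "The complete end of study (EOS) visit will be done via phone call 60 days post randomization". A later sentence of the same section adds that the call is made if applicable.
- Section 9.1.3, EOS Visit: "EOS visit will be conducted as a telephone visit", with the allowance that it, "if the patient is still hospitalized - can also be done at the clinic". The paragraph lists adverse events, outcome assessment, concomitant medication and counselling. It lists no blood draw.
- Section 9.1.3, day-35 visit, by contrast: "EDTA and heparin blood will be drawn to determine hemoglobin/platelets counts, D-dimer". The day-7 visit lists D-dimer in the same way.
- Time and Events Schedule: D-dimer is marked X at screening, day 7, discharge and day 35, but (X) at EOS. Hemoglobin/platelets, creatinine and the further safety bloods have no EOS entry. Footnote c says: "This visit may be performed as telephone visit".

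**The concern.** A telephone call cannot produce a D-dimer value. Followed as written, the plan gives a full set of draws at days 7 and 35. At day 60 it gives only what comes from patients still in hospital and from occasional optional draws. The model nevertheless treats day 60 as a visit like the others and reports a treatment difference there for the full analysis set.

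Two things are at stake. With few values the day-60 contrast carries almost no information. And the patients most likely to be measured are those still ill enough to be inpatients two months after randomization. A likelihood-based repeated-measures model handles missing values without bias only if missingness depends on what is in the model (baseline, day 7, day 35, strata). Hospital status at day 60 reflects current illness and is not in the model.

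**Working it through.** **1. Plan's own figure (section 11.7).** Inputs: log difference 0.44, SD 0.8, correlation with baseline 0.5, 40 per group, two-sided α = 0.05. Residual SD = 0.8 × √(1 − 0.5²) = 0.693. Noncentrality = 0.44 / (0.693 × √(2/40)) = 2.84. With 77 degrees of freedom the power is 80.1%, which matches the stated 80%. This concerns day 7 only; the protocol gives no figure for day 60.

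**2. Precision at day 60 by number of observed values.** The number is not in the documents, so a range is assumed, with an equal split between arms and the same residual SD. For a total of k values, half-width = t(0.975; k − 3) × 0.693 × √(2/(k/2)).

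| Day-60 values | Half-width of 95% CI, log units | As a ratio factor each way |
|---|---|---|
| 80 | 0.31 | 1.36 |
| 20 | 0.65 | 1.92 |
| 10 | 1.04 | 2.82 |
| 6 | 1.80 | 6.05 |

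For 10 values: 2.365 × 0.693 × √(2/5) = 1.04. For 6 values: 3.182 × 0.693 × √(2/3) = 1.80. Against the planning difference of 0.44, these half-widths are 1.04/0.44 = 2.4 and 1.80/0.44 = 4.1 times as large.

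**3. Bias, by reason for missingness.** Simulation of the maximum-likelihood repeated-measures estimate. Assumptions: 100 patients in two equal arms, SD 0.8 and correlation 0.5 throughout, true log differences −0.44 (day 7), −0.30 (day 35) and −0.20 (day 60), 3,000 runs, days 7 and 35 complete, randomization strata left out. The patients measured at day 60 are those with the highest day-35 values (missing at random given the model) or those with the highest day-60 values (selection on current state), each with some noise.

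| Share measured | Mechanism | Bias of difference | SE of difference | Bias of day-60 mean |
|---|---|---|---|---|
| 100% | – | about 0 | 0.14 | about 0 |
| 20% | by day-35 value | −0.01 | 0.345 | about 0 |
| 20% | by day-60 value | +0.12 | 0.21 | +0.88 |
| 10% | by day-35 value | about 0 | 0.64 | +0.03 |
| 10% | by day-60 value | +0.13 | 0.35 | +1.11 |

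Under the first mechanism the estimate is unbiased but loses most of its precision. Under the second, with 20% measured, the day-60 mean is too high by a factor of exp(0.875) = 2.4, and the true difference of −0.20 is estimated at about −0.20 + 0.12 = −0.08. With only 6 values the SE exceeds 1.5 under every mechanism tried, and the estimate could not be formed, because one arm had no value, in about 2% to 9% of runs.

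**4. Can the samples still be collected?** The amendment overview (section 18) says 111 patients were randomized by the hold on 11 June 2021 and that no further recruitment is planned. Day 60 for a patient randomized on that date is 10 August, or 14 August with the +4-day window. Amendment 1, which introduced this model, is dated 20 August 2021. All day-60 windows had closed by then, so only the analysis text can be changed.

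**The case against.** The protocol does not rule out day-60 blood draws. The schedule provides for optional D-dimer, physical examination and bio-bank sampling at EOS; footnote c says the visit may, not must, be by telephone; and the hospital exception does not say that only inpatients may attend. Nor are the visit descriptions complete: the discharge visit text omits D-dimer although the schedule marks it X. This stands. Some day-60 values may exist, and nothing in the documents fixes their number as near zero.

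A reader might infer several stronger conclusions that the documents do not support:

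- *That missing-at-random fails.* It is doubtful, because being measured probably depends on current illness, but that is not shown. The bias figures above come from selecting directly on the day-60 value, which is an assumed, unfavourable mechanism.
- *That the model will not converge and will spoil the day-7 and day-35 estimates.* Three of the six covariance parameters involve day 60, so this is a risk. It has not been demonstrated, and a fallback covariance structure is normal SAP content.
- *That nearly all day-60 values would be imputed.* Section 11.1 has one general sentence on multiple imputation. It does not say that longitudinal D-dimer is imputed before the MMRM, which can use incomplete records directly.
- *That the primary result is at risk.* The primary analysis in section 11.2 is a separate day-7 ANCOVA.

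It is also fair to say that poor precision would show in the reported interval. Selection bias would not.

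**Conclusion.** The mismatch stands in the current text: section 11.3 and the Synopsis promise a day-60 D-dimer contrast, while the visit plan makes day 60 a telephone visit with D-dimer at most optional. Day-60 values will probably come from a small, selected subset, and the contrast will then be very imprecise (half-width about 1.0 log units with 10 values, 1.8 with 6), biased, or both. The size depends on the unknown number of values and on why they were taken, and the figures borrow the day-7 planning SD and correlation.

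The point is moderate. The analysis is secondary, section 11 declares the trial explorative, and neither the primary endpoint nor the sample size depends on it. The ordinal scale at day 60 does not share the problem: the schedule marks it X at EOS, and it can be obtained by telephone.

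**What to change.** 1. In section 11.3 and the matching Synopsis text, restrict the D-dimer MMRM to days 7 and 35.
2. List any day-60 D-dimer values descriptively by arm, with hospital status at the time, and state that missing day-60 values are not imputed.
3. Align the EOS entry for D-dimer in the Time and Events Schedule with the EOS visit description in section 9.1.3, so that both say the same about whether, and for whom, a sample is taken.
4. Keep day 60 in the longitudinal analysis of the ordinal scale.

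The cost is wording, and no stated figure changes. The downside is that any optional day-60 values leave the model and are only described.

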Longitudinal D-dimer measurements assessed at day 7, 35 and 60 will be analyzed on the logarithmic scale using a mixed model for repeated measures (MMRM) approach. The model will include treatment, visit, treatment-by-visit interaction and stratification variables of the randomization as factors as well as logarithmic D-dimer baseline value as covariate. The residuals will be assumed to follow a multivariate normal distribution with unstructured covariance matrix. LS means of the group means and their differences will be computed for the various timepoints and reported with 95% confidence intervals.

Longitudinal ordinal data (seven-category ordinal scale) assessed at day 7, 35 and 60 will be analyzed using a proportional odds model with treatment, visit, treatment-by-visit interaction, baseline score and stratification variables of the randomization as factors. The correlation in longitudinal assessments within the same patient will be accounted for by random patient effects. Binary data (e.g. development of DIC) will use similar generalized linear mixed effect models but with logit link function.

All stratification variables of the randomization (site, gender (male, female, diverse), age (< 65 versus  $\geq$  65 years), kidney function (eGFR  $\geq$  30 mL/min/1.73m^2 and < 50 mL/min/1.73m^2 versus eGFR  $\geq$  50 mL/min/1.73m^2), history of CAD or heart failure (yes/no), oxygen demand on admission to the hospital (supplementary oxygen required versus not required), setting (outpatients versus hospitalized patients)) will be included as factors in the analyses of the secondary endpoints.

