## 11.7 Sample size determination

Sample size calculation is based on the primary endpoint D-dimer at day 7 corrected for baseline values. Since the distribution of D-dimer concentrations is skewed, calculations are done on the log scale. Using an analysis of covariance (ANCOVA) (significance level  $\alpha=0.05$  two-sided) with baseline values as covariate a total sample size of 80, i.e. 40 per group, gives a power of 80% to detect a mean difference of 0.44 (on the log scale) between the treatment group and the control group at day 7. Based on a blinded review, a common standard deviation of SD=0.8 and a correlation to baseline of  $r=0.5$  (both on the natural log scale) were assumed. The effect assumed translates to a reduction of 36% in D-Dimer values on the original scale. The co-primary endpoint is a seven-category ordinal scale previously recommended by the WHO (Attachment 2) as clinical improvement scale for patients with respiratory infections. Here 40 patients per group will give a power of 80% to detect a relative treatment effect  $p_1=0.68$  between treatment and control group at day 7 using a Wilcoxon (Mann-Whitney) rank-sum test (two sided,  $\alpha=0.05$ ). The probabilistic index or relative effect  $p_1$  denotes the probability that an observation in the treatment group will be less than an observation in the control group. Targeting a total of at least 80 evaluable patients, we aim to recruit about 100 patients.

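### The longitudinal D-dimer model fixes one baseline slope for all visits; if the slope changes after day 7, the visit-specific differences lose some precision and keep part of any chance baseline imbalance

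*Protocol*

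**What the plan says.** Protocol section 11.3 states: "Longitudinal D-dimer measurements assessed at day 7, 35 and 60 will be analyzed on the logarithmic scale". The fixed effects are "treatment, visit, treatment-by-visit interaction and stratification variables of the randomization as factors as well as logarithmic D-dimer baseline value as covariate". On the covariance it says: "The residuals will be assumed to follow a multivariate normal distribution with unstructured covariance matrix". On what is reported it says: "LS means of the group means and their differences will be computed for the various timepoints and reported with 95% confidence intervals". The Synopsis (Secondary Efficacy Endpoints) repeats the model, again entering the baseline value once, "as factors as well as logarithmic D-dimer baseline value as covariate". No baseline-by-visit term is named in either place.

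The primary day-7 comparison is a separate ANCOVA (section 11.2), which adjusts for log baseline at day 7 alone. Section 11.7 gives the only figures on baseline: "a common standard deviation of SD=0.8" and a correlation of 0.5 between baseline and day 7, both on the natural log scale. Nothing is given for day 35 or day 60.

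**The concern.** The model frees the treatment effect and the residual covariance at each visit but ties the baseline slope to one value. The slope at a visit is the correlation with baseline times the ratio of that visit's SD to the baseline SD, so it changes if either the correlation or the spread changes. Most patients are to enter because D-dimer is raised in acute illness. It is natural, though not documented, to expect baseline to say less about day 35 than about day 7.

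If so, the fitted slope is too flat for day 7 and too steep for day 35. Each visit-specific difference is itself a reported result. Baseline D-dimer is not among the randomization factors, so chance imbalance in it is handled mainly through this covariate. What is at stake is the precision of the secondary day-7 and day-35 estimates, and how well each is corrected for the baseline imbalance that happens to occur.

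**Working it through.** **Inputs from section 11.7.** Two-sided alpha 0.05, 40 per group, difference 0.44, SD 0.8, baseline to day-7 correlation r7 = 0.5.

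**Assumed, not in the protocol.** Baseline SD 0.8; day-35 correlation with baseline r35 from 0 to 0.5; day-35 SD of 0.8 or 0.5; day-7 to day-35 correlation ρ from 0.3 to 0.7; two visits with complete data.

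**The plan's own figure.** The ANCOVA residual variance is 0.8² × (1 − 0.5²) = 0.48. Then n per arm = 2 × (1.960 + 0.842)² × 0.48 / 0.44² = 38.9, so 39. With 40 per arm, power is 81.1% by the normal approximation and 80.1% by the noncentral t distribution with 77 df. The reduction is 1 − exp(−0.44) = 35.6%, which agrees with the stated 36%. The sample size reproduces. The protocol states no figure for the longitudinal model.

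**What a common slope does.** Let β7 and β35 be the true slopes, v7 and v35 the residual variances, and c the residual covariance. With an unstructured covariance and complete data, the fitted common slope is

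b = [(v35 − c)β7 + (v7 − c)β35] / [(v35 − c) + (v7 − c)].

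At visit t, the share of a baseline difference left in the treatment estimate is βt − b. The variance ratio against a model with a slope per visit is 1 + (βt − b)² × 0.8² / vt.

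**Worked case: r35 = 0, ρ = 0.3, SD 0.8 at both visits.** β7 = 0.5 and β35 = 0; v7 = 0.48 and v35 = 0.64; c = 0.3 × 0.64 − 0 = 0.192. Then b = 0.5 × 0.448 / (0.448 + 0.288) = 0.304. Left over at day 7: 0.196, variance ratio 1 + 0.196² × 0.64 / 0.48 = 1.051. Left over at day 35: −0.304, variance ratio 1 + 0.304² × 0.64 / 0.64 = 1.093.

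**Range over ρ = 0.3 to 0.7:**

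| Day-35 SD | r35 | Common slope | Variance ratio, day 7 | Variance ratio, day 35 |
|---|---|---|---|---|
| 0.8 | 0.5 | 0.50 | 1.00 | 1.00 |
| 0.8 | 0.3 | 0.41-0.43 | 1.007-1.010 | 1.014-1.018 |
| 0.8 | 0.2 | 0.37-0.41 | 1.010-1.021 | 1.032-1.047 |
| 0.8 | 0 | 0.30-0.43 | 1.007-1.051 | 1.093-1.184 |
| 0.5 | 0.5 | 0.32-0.36 | 1.03-1.05 | 1.00-1.01 |
| 0.5 | 0.2 | 0.13-0.23 | 1.10-1.19 | 1.00-1.03 |

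The fifth row shows that equal correlations are not enough. With unequal SDs the slopes are 0.50 and 0.5 × 0.5 / 0.8 = 0.31.

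**Leftover imbalance.** One standard error of the baseline difference at 40 per arm is 0.8 × √(2/40) = 0.179 log units. With SD 0.8 at both visits, an imbalance of that size shifts the estimates by:
- r35 = 0.3: +0.013 to +0.016 at day 7 and −0.020 to −0.023 at day 35;
- r35 = 0: +0.013 to +0.035 at day 7 and −0.054 to −0.077 at day 35.

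With day-35 SD 0.5 and r35 = 0.2, the day-7 shift is 0.268 × 0.179 = 0.048 up to 0.375 × 0.179 = 0.067. The planned day-7 effect is 0.44.

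**Simulation check.** With 40 per arm, SD 0.8 at both visits, ρ of 0.3 or 0.5 and 3,000 trials per scenario, the simulated variance ratios and leftover shares were close to the formula. With equal slopes the ratio was 0.99-1.00. The estimates averaged close to zero error in every scenario.

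**The case against.** **The premise is assumed.** The protocol does not say that the slope changes, and it says nothing about day-35 spread; the SD of 0.5 is an illustration. This stands, and the point is therefore conditional. A reader might infer from the model statement that precision is lost in any case. The documents do not support that: with equal slopes nothing is lost.

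**The effect is small and secondary.** With equal SDs and a modest fall in correlation, the cost is 1-2% in variance. The analysis is secondary, in a study that calls its own analyses explorative. This also stands and limits the weight of the point.

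**It is a matter for the statistical analysis plan.** Section 11 leaves further detail to that document, which is not at hand and may add the term. But the protocol gives an explicit term list, and a plan that follows it inherits one slope.

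**A separate day-60 slope has a price.** The Synopsis makes day 60 a telephone visit, and the Time and Events Schedule marks D-dimer there as optional, so few values are likely. In a three-visit simulation with equal slopes and an assumed 20% of patients having a day-60 value, freeing all slopes raised the day-60 variance by roughly 8-10%. This stands and shapes the fix.

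**The fix does not align the two day-7 results.** A reader might infer that a baseline-by-visit term makes the day-7 contrast equal to the primary ANCOVA. It would not. The seven stratification factors also enter the mixed model without visit interactions, and section 11.1 plans multiple imputation for missing values, whereas a mixed model can borrow from later visits.

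**Conclusion.** The point holds in conditional form. As written, the model has one log-baseline slope for days 7, 35 and 60. If the true slope differs between visits, the day-7 and day-35 differences are each adjusted by a compromise.

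With SD 0.8 at both visits, the variance cost is about 1% at day 7 and 1-2% at day 35 if the day-35 correlation is 0.3. It is 1-5% and 9-18% if that correlation is 0. With an assumed day-35 SD of 0.5 and correlation 0.2, it is about 10-19% at day 7. It is nil if the slopes are equal. These figures rest on two visits, complete data and the assumed range of 0.3 to 0.7 for the correlation between visits.

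Two stronger readings should be resisted. The leftover imbalance is not a bias: it is a shift given the imbalance that occurred, and it averages to zero over randomizations. Nor does the primary result suffer: the ANCOVA fits its own day-7 slope, and the sample size rests on that ANCOVA. This is an inexpensive improvement to a secondary model, not a flaw in the trial's main conclusion.

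**What to change.** In section 11.3 and in the matching Synopsis paragraph, add an interaction of log baseline D-dimer with visit to the fixed effects of the longitudinal model. State that if few day-60 values are available, the term will be limited to separate slopes for day 7 and day 35, with the rule for day 60 fixed before treatment-group results are seen. Do not describe the change as making the day-7 contrast agree with the primary ANCOVA.

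The cost is one degree of freedom per additional visit, and an imprecise day-60 slope if that visit is given its own. No new data are needed. If the slopes turn out equal, the loss at days 7 and 35 is about 1% in variance or less.
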